13.4.4. Secondary Efficacy Analyses

Secondary efficacy analyses will be based on the ITT population only. For PGIC, patients with a “very much improved” or “much improved” response at the Week 14 endpoint will be considered responders. Patients with results in any other category or who discontinue early will be considered non-responders. PGIC responder status (yes/no) will be analysed using logistic regression with treatment and site as categorical effects. In addition, odds ratios and corresponding 95% confidence intervals will be presented.

Analysis of continuous secondary endpoints and adjustments for missing data will be described in detail in the SAP. Significance tests of treatment differences will be tested at the two-sided 0.05 level and corresponding 95% confidence intervals will be calculated.

To adjust for multiplicity and to control for overall type I error, a sequential test procedure will be applied to the efficacy endpoints. If the primary analysis produces a result that is statistically significant at the 0.05 level, a significance level of 0.05 will be used for comparing the secondary endpoints in an ordered fashion. If the analysis for a secondary endpoint does not produce a statistically significant result at the 0.05 level, then the remaining secondary endpoint analyses will automatically be considered non-significant regardless of the p-value produced. The order in which the secondary endpoints are to be tested will be specified in the SAP.

No other adjustments for multiplicity will be made and other p-values displayed in the output will be considered for descriptive summary purposes only and will not be used for formal inference. Full details regarding the statistical analyses for the listed endpoints, including graphical presentations, can be found in the SAP.

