5. ANALYSIS AND REPORTING

5.1 Interim Analysis

An optional interim analysis may be performed when approximately 50% of the initially planned enrollment is evaluable for efficacy assessments. This interim analysis will be performed by an unblinded team separate from the team responsible for the conduct and analysis of the study. An Independent Data Monitoring Committee (IDMC) will review the data and recommend to the Sponsor one of the following:

- Stop the study early for efficacy [REDACTED]
- Increase the sample size by a fixed amount
- Keep the current sample size and continue as planned
- Stop the study early for futility [REDACTED]
[REDACTED]

[REDACTED]
[REDACTED]
[REDACTED]
[REDACTED]
[REDACTED]
[REDACTED]
[REDACTED]
[REDACTED]
[REDACTED]
[REDACTED]
[REDACTED]

The interim analysis will be conducted approximately 18 weeks after randomization of approximately 236 participants, i.e. when approximately 50% of the initially planned participant enrollment (470) is evaluable for efficacy assessments (approximately 14 weeks); and related data cleaning, database freeze, and administrative tasks have been completed on this cohort (approximately 4 weeks).

In the case of an early stop for futility or efficacy, initial results may be released prior to full database lock; however, clinical study report (CSR) results will be based on the final analysis described below.

[REDACTED]
[REDACTED]

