8. GENERAL ISSUES FOR STATISTICAL ANALYSIS

8.1 General Statistical Methodology

Descriptive summaries will be provided where appropriate for each of the primary and secondary variables. In general, tables will summarize data by treatment group and visit. All subjects for a population in each treatment group will be grouped together; subjects that reduce dose from two tablets per day to one tablet per day will not be reported separately for the analyses described in this SAP, unless otherwise noted. If there are more than 10 subjects in the active arm with a dose reduction at any point in the study, summary statistics on key outcomes may be reported for subjects with dose reductions.

Baseline characteristic and safety tables will be completed for the Safety Population unless otherwise specified. Efficacy tables will be presented for the ITT Population.

Continuous, quantitative variable summaries will include the number of subjects (N) with non-missing values, mean, standard deviation, median, minimum, and maximum.

Categorical, qualitative variable summaries will include the frequency and percentage of subjects who are in the particular category. In general, the denominator for the percentage calculation will be based upon the total number of subjects in the study population for the treatment group unless otherwise specified.

Baseline values are defined as the last non-missing measurement prior to the first dose of study drug. For scores obtained via diary, baseline will be defined as the average of the scores from the 7 days prior to the baseline visit. Change from baseline will be defined as the post-baseline visit value minus the baseline value.

Study day is defined as assessment date – first dose date +1.

All analyses will be performed using SAS[®] Software version 9.3 or later.

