8.1.1.2 Multiplicity

To adjust for multiplicity and to control for overall type I error, a sequential test procedure will be applied to the primary and key secondary efficacy endpoints. If the primary analysis produces a result that is statistically significant at the two-sided [REDACTED] level, a significance level of [REDACTED] will be used for comparing the secondary endpoints in an ordered fashion. If the analysis for a secondary endpoint does not produce a statistically significant result ([REDACTED]), then the remaining secondary endpoint analyses will automatically be considered non-significant regardless of the p-value produced. [REDACTED]

The order of key secondary endpoints in which they are to be tested is as follows:

- Proportion of subjects with a PGIC rating of “very much improved” or “much improved” at Week 14
- Change from baseline in the FIQR symptoms domain score at Week 14
- Change from baseline in the FIQR function domain score at Week 14
- Change from baseline in the PROMIS score for sleep disturbance at Week 14
- Change from baseline in the PROMIS score for fatigue at Week 14
- Change from baseline to Week 14 in the weekly average of the daily diary assessment of sleep quality.

No other adjustments for multiplicity will be made and other p-values displayed in the output will be considered for descriptive summary purposes only and will not be used for formal inference. Additional details regarding statistical analysis for the listed endpoints can be found in [Section 10](#).

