8.1.3 Imputation of Missing Data

For individual daily pain scores, since a mean is used in the calculation of the primary endpoint, it is not necessary to replace values missing on random intermittent days; weeks will have average values as long as a single value for that week is present.

Missing weekly pain scores for participants in the ITT population will be imputed via multiple imputation (MI). When the study medication was discontinued due to lack of efficacy (LOE) or due to an AE, missing values will be imputed drawing from the baseline values, conditioned on the non-missing weekly average post-baseline values, of all participants in the ITT population under the assumption that they are missing not at random (MNAR), with a covariate for site. If the study medication was discontinued for any other reason (including impacts from the COVID-19 pandemic), values will be imputed within treatment group using MI under the assumption that they are missing at random (MAR) with covariates for site and the average pain severity score recorded at each time point. The MAR approach will also be applied for sporadic missing values (prior to discontinuation). The MI process will use twenty repeats in the analysis datasets generated; seeds are given in [Appendix D](#). For the purposes of the MI, all sites with less than 10 subjects will be pooled into a single large site; this will be done for both the interim and post interim samples.

The steps will be as follows:

1. Intermittent missing weekly average scores will first be imputed using the Markov Chain Monte Carlo (MCMC) method implemented with the SAS MI procedure, which is appropriate for non-monotonic missing data.
2. For subjects that do not discontinue for LOE or AEs, a MAR imputation will be applied: the monotone missing values will then be multiply imputed with the SAS MI procedure using the monotone regression method. Baseline average and the weekly scores will be included as covariates as well as site; imputation will be done within treatment group.

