3. For subjects that discontinue for LOE or AEs, an iterative process will be applied moving through each week. The complete MAR dataset from step 2 above will be used and augmented with subjects missing for the week being imputed at that stage. The non-missing values for the week in question will temporarily be set to the subjects corresponding baseline value, so the data from LOE and AE subjects are imputed for that week drawing from the baseline distribution. This will proceed from Week 1 to Week 14 with the imputed complete dataset for a week serving as the basis for the subsequent week. Covariates at each stage will include the values for the prior weeks (observed, MAR imputed in steps 1& 2, or imputed previously in this step) and site.

The above process will be done independently for the subjects included in the interim analysis and those not in the interim.

Daily sleep diary data will be handled in an identical manner to the pain scores.

Continuous outcomes included in the list of key secondary outcomes that are collected in-clinic will be handled as above, minus the step of creating weekly averages of daily values and with steps being done by visit instead of week.

Subjects with missing PGIC at a given visit will be considered non-responders at that visit for the purposes of treatment comparisons and efficacy claims; additional tabulations will summarize the number and percentage in each category out of non-missing values as well as a count of the missing values.

No missing safety data will be imputed.

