10.2 Secondary Efficacy Analyses

Secondary efficacy analyses will be based on the ITT population only.

Continuous Endpoints

For the purposes of possible label claims and reported p-values entered into the multiplicity algorithm, an approach identical to the primary analysis will be used for all continuous outcomes. See [Section 8.1.3](#) for the imputation algorithm and [Section 10.1.2](#) for the analysis approach.

Outcomes using these analyses will include:

- Change from baseline in the FIQR symptoms domain score
- Change from baseline in the FIQR function domain score
- Change from baseline in the PROMIS score for sleep disturbance
- Change from baseline in the PROMIS score for fatigue
- Change from baseline in the weekly average of the daily diary assessment of sleep quality.

For each, all time points will be summarized, but the primary time point of interest is Week 14. Time points other than Week 14 are considered exploratory. The estimand for each is identical to the primary, substituting for the endpoint in question.

For the sleep quality assessment collected via a daily subject diary, the baseline score and the weekly scores for each subject will be calculated as the weekly average score based on the mean of the scores recorded for that study week ([Section 8.2.2](#)).

This will be repeated on the outcomes above, but using observed data only without imputation.

Categorical Endpoints

A categorical analysis of PGIC will be performed using a logistic regression model for each week with effects for treatment and investigative site. If the model does not converge, site will be removed from the model. Subjects with results of “very much improved” or “much improved” (defined as responders) will be compared to all other categories (defined as non-responders). Subjects with missing data will be considered non-responders. In addition, odds ratios and corresponding 95% CI intervals for being “very much improved” or “much improved” versus all other categories will be presented. A summary of frequency counts for PGIC responses for each time point will be presented; Week 14 is of primary interest and all other time points are considered exploratory.

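### PGIC, the first key secondary: an undefined non-convergence rule decides between a mildly anti-conservative site-adjusted logistic fit and an unadjusted one

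*SAP*

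**What the plan says.** - **Model.** Protocol 13.4.4: "PGIC responder status (yes/no) will be analysed using logistic regression with treatment and site as categorical effects". It gives no fallback. SAP 10.2 (Categorical Endpoints) uses the same model and adds one: "effects for treatment and investigative site. If the model does not converge, site will be removed from the model". The SAP does not use the word fixed, but a plain logistic regression with site as a categorical effect is most naturally read that way.
- **Software.** SAP 8.1 states "All analyses will be performed using SAS" and gives a version. Nothing names a procedure, a convergence criterion, or the treatment of a site with no responders or only responders.
- **Missing PGIC.** SAP 8.1.3: "Subjects with missing PGIC at a given visit will be considered non-responders at that visit". All randomized patients therefore enter the model and PGIC is not multiply imputed.
- **Pooling.** SAP 8.1.3: "For the purposes of the MI, all sites with less than 10 subjects will be pooled into a single large site". No such rule is given for the PGIC model.
- **Testing order.** SAP 8.1.1.2 places PGIC first among the six key secondaries, after a significant primary. Protocol 13.4.4 gives the level: "a significance level of 0.05 will be used for comparing the secondary endpoints in an ordered fashion". The SAP level is redacted.
- **Randomization.** Protocol 7.3 stratifies it by center.

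**The concern.** Maximum-likelihood logistic regression with a separate intercept for each small stratum pushes the treatment log odds ratio away from zero, and the standard error does not fully compensate. With site kept, the test is then mildly anti-conservative and the odds ratio too large.

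The fallback adds a different problem. A site in which everyone or no one responds has no finite maximum-likelihood site coefficient. Some convergence criteria call such a fit converged and others do not. If it counts as non-convergence, site leaves the model and the reported analysis becomes an unadjusted one that ignores the randomization stratum. The data and an unstated software setting then choose the analysis.

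PGIC is the gate to five further key secondaries, and its odds ratio will be reported as an effect size. The excess error matters when the primary effect is real and PGIC has none; under the global null, the primary gate caps it.

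**Working it through.** **Inputs from the documents.** N = 470, 1:1; 35 to 45 sites; randomization stratified by center; two-sided 0.05 (Protocol level, illustrative because the SAP level is redacted).

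**Assumed, because the documents do not give them.** Placebo response 20-40%; between-site SD 0.4 on the logit scale; blocks of four; even or uneven site sizes; true odds ratio 1.70 for bias and power. The plan states no PGIC response rate, odds ratio or power, so it has no figure to reproduce.

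**1. Site size.** 470/45 = 10.4 and 470/35 = 13.4 patients per site, with 34 to 44 site parameters.

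**2. How often an all-or-none site occurs.** Hand check with identical sites, 25% response, 40 sites of about 12 patients:
- P(no responders at a given site) = 0.75^12 = 0.032.
- P(at least one such site) = 1 − (1 − 0.032)^40 ≈ 0.73.

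Site variation raises this. Simulated with SD 0.4 and even sites, under the null:

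| Response | 35 sites | 40 sites | 45 sites |
|---|---|---|---|
| 20% | 93% | 98% | 99.8% |
| 25% | 74% | 89% | 97% |
| 30% | 49% | 69% | 85% |
| 40% | 14% | 27% | 43% |

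With uneven sites it is 96-100%.

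**3. Whether such a fit converges.** Five example datasets, each with 2 to 8 all-or-none sites, were fitted in a general GLM routine (not SAS). All five converged on a deviance criterion, with a largest site coefficient of 21.9 to 24.0 in absolute value. All five failed on a parameter criterion. The answer depends on a setting that the SAP does not state.

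**4. Operating characteristics, single fit.** Type I error is the share of null trials with two-sided p < 0.05. The reported odds ratio is exp(mean log OR) at a true 1.70.

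| Analysis | Type I error | Reported OR |
|---|---|---|
| Site kept | 5.2-6.4% | 1.76-1.81 |
| SAP rule, all-or-none site = non-convergence | 4.3-5.6% | 1.67-1.78 |
| Site always dropped | 4.4-4.9% | 1.64-1.69 (site SD 0 to 0.6) |
| Site-stratified CMH | 4.4-5.4% | 1.69-1.72 |
| Conditional logistic, stratified by site | 4.9-5.4% | 1.69-1.71 |

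The largest runs for site kept (20,000 null trials in each of 24 settings, Monte Carlo SE 0.17 points) gave 5.6-6.3%. In smaller runs (8,000 null trials, SE about 0.24 points), single settings reached 6.8% with site kept and 5.8% under the second row. The 5.8% arose at 40% response with even sites, where all-or-none sites are rarest and site is mostly retained.

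**5. Size of the bias.** 1.76/1.70 = 1.035 and 1.81/1.70 = 1.065, so 3.5-6.5% too high. On the log scale, ln(1.78/1.70) = 0.046, against a standard error of 0.20-0.23: about 0.2 of a standard error.

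**6. What the trigger changes.** Keep-site and drop-site verdicts differ in 1.3-1.8% of null trials and 3.2-4.8% of trials at OR 1.70. Rejecting when either is significant gives 5.8-6.4%, at most about 0.2 points above keeping site.

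**7. Power cost of the alternative.** At OR 1.70, site kept has 69.4-82.2% and CMH 67.4-80.2%. To see how much of that gap is inflation, take a valid test with 73.7% power: Φ(δ − 1.960) = 0.737 gives δ = 2.594. Run at 6.0% (critical value 1.881), it shows Φ(2.594 − 1.881) = 76.2%, a gain of 2.5 points.

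**The case against.** The strongest objection is that SAP 10.2 specifies a two-step rule, not simply a site-adjusted model. A reader might infer from the site-kept row that the planned PGIC test has a 6% type I error and overstates the odds ratio by 5%. The documents do not support that without a condition. Counting an all-or-none site as non-convergence is a natural reading of the rule, and under it both the inflation and the upward bias largely disappear. The opposite reading is not established either, because the trigger is left open. This objection stands, and the point is worded accordingly.

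A reader might also infer that the fallback is itself a source of inflation. It is not: dropping site gives 4.4-4.9%, and even choosing the better of the two results adds almost nothing. It is a reproducibility gap.

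A third tempting step is to quote stage-wise figures. If PGIC is fitted by stage (about 5 to 7 patients per site per stage) and combined by inverse normal, site kept gives 6.4-7.8% with stages of 236 and 234. Protocol 13.6 describes combination for the key secondaries generally, and SAP 8.1.1.1 in the case of a sample size increase. But SAP 5.1 says "An optional interim analysis may be performed when approximately 50% of the initially planned enrollment is evaluable", and the surrounding text is partly redacted. These figures are conditional and carry no weight in the severity here.

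Finally, every magnitude rests on assumed inputs. That is fair. The direction is stable over the ranges tried, but the exact percentages are not properties of the documents.

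**Conclusion.** The point holds in conditional form. If site is retained, type I error is about 5.2-6.4% at nominal 5%, and a true odds ratio of 1.70 is reported as about 1.76-1.81. If an all-or-none site counts as non-convergence, the figures are about 4.3-5.6% and 1.67-1.78, and the estimate is mostly unadjusted for the randomization stratum. The SAP does not say which applies, so the reported test and odds ratio depend on an undefined trigger.

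The practical effect is modest and would seldom reverse the PGIC result. The textual gap is certain; the sizes depend on the assumed response rate, site variation, block size and site-size distribution, and on 5% as the level. This is a cheap improvement, held with moderate confidence.

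**What to change.** In SAP 10.2, replace the PGIC model and its fallback with one pre-specified analysis. Conditional logistic regression stratified by site is closest to Protocol 13.4.4. A site-stratified CMH test with the Mantel-Haenszel common odds ratio and 95% CI is the alternative. Both match the stratified randomization, and an all-or-none site simply contributes no information on treatment. Delete the sentence that removes site, apply the same method within each stage if stages are combined, and record the change in SAP Section 13.

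Two lesser changes fall short. Defining non-convergence closes the reproducibility gap but leaves either the anti-conservative fit or the unadjusted one. Extending the under-10 pooling rule to PGIC gives 5.1-5.8% with uneven sites; with even sites it pools nobody (470/45 = 10.4) and leaves 5.7-6.3%.

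Changing the responder models in SAP 10.3 is optional, because SAP 8.1.1.2 says "other p-values displayed in the output will be considered for descriptive summary purposes only".

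The cost is a few lines of text and code, and about 1 to 4 points of nominal power at OR 1.70 against the site-kept fit, roughly what the inflation adds. The odds ratio would be about 5% less favourable than the site-kept one.

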10.3 Exploratory Analyses

All efficacy analyses at time points other than Week 14 are considered exploratory as described above.

Additional exploratory efficacy endpoints include:

- FIQR total score, overall impact domain score, and individual item scores at all post-randomization clinic visits
- Proportion of subjects with a $\geq 30\%$ improvement from baseline to Weeks 1-14 in the daily self-reported pain severity score
- Proportion of subjects with a $\geq 50\%$ improvement from baseline to Weeks 1-14 in the daily self-reported average pain severity scores
- PGIC as a continuous variable with 1-7 scoring
- CSFQ-14 at Week 14
- In-clinic assessment of pain (24-hour & weekly recall)
- Permutation test of change from baseline in the weekly average of the daily pain scores at week 14.

The proportion of improvement endpoints will be analyzed in using a logistic regression model for each week with effects for treatment and investigative site. If the model does not converge, site will be removed from the model. Subjects with missing data will be considered non-responders. In addition, odds ratios and corresponding 95% CI intervals for being a pain responder will be presented.

In addition to the responder analysis in the secondary outcomes, PGIC will be analyzed as a continuous variable scoring the responses 1-7. Results will be reported by treatment with summary statistics and an MMRM Model will be used to compare treatments. The model will include the fixed, categorical effects of treatment, site, study week, and treatment by study week interaction. An unstructured covariance structure will be used to model the within-subject errors. If this analysis fails to converge, the following structures will be tested in this order: first order ante dependence, heterogeneous first order autoregressive, heterogeneous compound symmetry and compound symmetry with the first to give convergence used. The Kenward-Roger approximation will be used to estimate the denominator degrees of freedom. Significance testing will be based on least-squares means using a two-sided $\alpha=0.05$ test and two-sided 95% confidence intervals will be presented.

The CSFQ-14 is completed at baseline and Week 14/ET. It has a male and a female version, which will be analyzed separately. The CSFQ-14 will be analyzed for its total score, three subscales on phases of sexual response, and five subscales for dimensions of sexual functioning by using an Analysis of Covariance (ANCOVA) model. The model will include the fixed, categorical effects of treatment and site, plus a baseline covariate corresponding to the subscale (or total) being analyzed. Significance testing will be based on least-squares means using a two-sided $\alpha=0.05$ test and two-sided 95% confidence intervals will be presented. This outcome is considered to be supportive of the product's safety; other exploratory analyses are for further support of product efficacy.

The FIQR exploratory endpoints and the in-clinic pain assessments will be analyzed using an MMRM including the fixed, categorical effects of treatment, site, study week, and treatment by study week interaction, as well as the fixed covariates of baseline value and baseline value score-

by-study week interaction. An unstructured covariance structure will be used to model the within-subject errors. If this analysis fails to converge, the following structures will be tested in this order: first order ante dependence, heterogeneous first order autoregressive, heterogeneous compound symmetry and compound symmetry with the first to give convergence used. The Kenward-Roger approximation will be used to estimate the denominator degrees of freedom. Note that the screening values will be used as baseline for the in-clinic pain outcomes.

